2. To assess the safety of extending the interval of INR follow-up in patients.

Hypothesis: We hypothesize that there will not be a difference between the bleeding and thromboembolic events from baseline (12 months prior to study enrollment) to events/year at 6, 12, and 24 months.

Hypothesis: We hypothesize that there will not be a difference in the patient's time in therapeutic range (TTR) from baseline (12 months prior to study enrollment) compared to the TTR at 12 and 24 months.

3. To examine patients' and providers' acceptance of the intervention (to extend the follow-up interval of INR monitoring).

Hypothesis: We hypothesize that both patients and providers will favorably view the intervention.

Background:

Anticoagulation treatment with vitamin K antagonists, such as warfarin, can be complicated by many variables, such as drug interactions, diet, health status, other medications, and adherence. Frequent INR monitoring is required to keep patients' INR values within their target therapeutic range to lower the risk of hemorrhagic or thrombotic adverse events. However, some patients remain on the same warfarin dose with INRs within their goal range for extended periods of time. Predictors of very stable INR control for patients on long-term anticoagulation with warfarin include age greater than 70 years, male gender, INR target less than 3.0, and absence of heart failure, diabetes, or other chronic diseases.^{1, 2}

The most recent American College of Chest Physicians 2012 guidelines recommend an INR testing frequency of up to 12 weeks over 4 weeks in patients on warfarin with consistently stable INRs (Grade 2B; weak recommendation, moderate-quality evidence).³ The guidelines define stable INRs as at least 3 months of INRs that are within therapeutic range, thus not requiring changes in warfarin dose. These guidelines are now more comparable to those from the United Kingdom, where the practice of a 12-week INR monitoring interval has been usual practice.⁴ Despite the guideline recommendations, many United States anticoagulation providers are hesitant to extend the duration of INR follow-up to 12 weeks, as historically, the recommended interval and standard clinical practice for INR follow-up was a maximum of 4-6 weeks.

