within goal INR range for 6 or 12 months, to other patients, defined as one or more INRs outside of goal range during a 6 or 12 month period.^{1,2} Both studies found that bleeding and thromboembolic events were significantly lower with stable patients compared to the other patients on warfarin. Schulman et al. found no difference between the 4-week and 12-week groups in regards to major bleeding events, objectively verified thromboembolic events, and death.¹⁰ Schulman defined bleeding events per previously published criteria.¹¹ Although the Schulman et al study demonstrated favorable results, it is unknown if the patient contact every 4 weeks contributed to the positive outcomes. Additionally, the anticoagulation population in a VA Anticoagulation Clinic may be different (increased age, more comorbidities). Thus, we propose to examine an extended interval of INR follow-up in eligible patients at the William S. Middleton Memorial Veterans Hospital.

The Anticoagulation Clinic at the William S. Middleton Memorial Veterans Hospital and its associated community-based outpatient clinics is a pharmacist-managed service. The clinic currently follows approximately 1800 unique patients. The clinic manages the initiation of antithrombotic therapy, follows patients on short-term and long-term antithrombotic therapy, manages the transition from inpatient to outpatient care, and coordinates warfarin interruptions for procedures using low-molecular weight heparin if warranted. During an initial visit to the clinic, patients are oriented to warfarin as well as clinic procedures. A patient and provider responsibilities document is reviewed with all patients. For subsequent visits and INR assessments, patients are either seen in clinic or receive follow-up by telephone. The maximum interval between INRs is currently 5-6 weeks. Pharmacists have prescriptive authority under a scope of practice. This type of clinic is similar to other anticoagulation clinics in the Veteran Affairs system nationally and is considered high-quality anticoagulation management.¹²

Methods and Procedures

Design:

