A prospective cohort study is proposed to assess the feasibility, safety, and acceptability of extending the interval of INR follow-up to 12 weeks in stable warfarin patients. All participants consenting to study participation will have their INR follow-up interval extended according to the study protocol. If a participant's warfarin dose and INRs continue to be stable, the follow-up interval will be extended from 5-6 weeks, to 7-8 weeks, and then to 11-12 weeks. Participants will be surveyed to explore their opinions and satisfaction with the changes to their follow-up interval at various points in the study (baseline, 6 months, 12 months, 24 months). At the end of the study, a focus group will be held for a random subset of participants to obtain further information related to acceptability of this type of follow-up.

Additionally, we plan to assess anticoagulation clinic provider study staff's knowledge of the study protocol prior to the enrollment of participants for quality improvement and programmatic evaluation. At the end of the study, we also plan to hold a focus group for all anticoagulation clinic provider study staff to obtain further information related to the extended INR interval follow-up process.

Participants: We propose to enroll 75 eligible patients on warfarin from the William S. Middleton Memorial VA Hospital in Madison, WI and the Madison VA's associated community-based outreach clinics. Patients must also meet the following criteria to be invited to participate:

- 18 years of age or older
- requirement for indefinite warfarin therapy
- target INR of 2-3

- stable weekly warfarin dose for the past 6 months
 - not more than a single, one-time adjustment (boost/omission) in the past 6 months
 - planned interruption for a procedure or surgery with INR(s) out of range in the past 6 months would not exclude a patient
 - a patient of the Madison VA anticoagulation clinic for the previous 12 months
- Patients will not be eligible to participate in the study if they meet any of the following criteria:
- consistently drink ≥ 4 alcoholic beverages/day or a documented episode of alcohol binging in the past 6 months
 - diagnosis of cancer and on active chemotherapy/radiotherapy in the past 3 months
 - life expectancy of < 1 year
 - enrolled in other investigational drug protocols
 - only receiving anticoagulation care at the Madison VA for part of the year (e.g. snowbirds)
 - receiving visiting nurse services for INR monitoring

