 - thrombocytopenia ($< 100K$) within past 12 months
 - history of bleeding or thromboembolism requiring medical intervention within past 6 months
 - treatment for active liver disease (e.g. hepatitis)
 - diagnosis or documentation in EMR suggesting cognitive impairment
 - activated power of attorney
 - inability to provide informed consent
 - non-English speaking
 - unstable mental health disorder that impairs judgment
 - history of non-adherence to anticoagulation clinic policies and procedures (i.e. missed appointments, self-adjustment of warfarin dose, nonadherence, etc.).

Procedures:

Patient identification: A study staff member will review anticoagulation clinic patients' electronic medical records (EMR) for eligibility criteria prior to each appointment day until 75 patients are enrolled in the study or 3 months has elapsed. A list of eligible patients will be provided to study staff so they are aware that a patient is eligible prior to interacting with the patient during a routine clinic visit. After the initial group of patients has completed 6 months in the study and after a safety review, additional patients may be enrolled if 75 patients were not initially enrolled.

Patients who are eligible will be invited to participate in a research study, either face-to-face or over the phone, depending on the type of anticoagulation clinic visit. If they are interested, they will be provided information on the study requirements during that anticoagulation clinic visit. Potential participants will have the opportunity to ask questions they have regarding the study and the consent process initiated. Participants will not be paid for participation in the study. Subjects who receive phone calls and utilize secure messaging as part of their anticoagulation clinic visits will first receive an invitation letter by mail. At the subsequent anticoagulation clinic visit, they will be introduced to the study during a phone call. A separate recruitment call will not be made.

Face-to-face visit: For a face-to-face clinic follow-up visit, the informed consent, participant responsibilities agreement, and HIPAA authorization form will be reviewed and the patient will be provided with two copies of these documents. One copy of these documents will be collected during the visit and the patient will keep one copy. Once the documents are reviewed and signed, the patient will be considered enrolled in the study. The extended interval protocol

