- Fatal or symptomatic bleed into a critical area or organ
- Bleeding leading to hospitalization
- Transfusion of 2 units or more packed red blood cells

Serious

- Bleeding leading to ED or UC visit or additional testing

After a major bleed, the participant will be removed from the extended follow-up interval and will not be eligible to qualify for the extended follow-up interval for 6 months after the event. After a serious bleed, the patient will be managed with usual care. If they did not have a permanent weekly dose change or if the temporary dose change was less than or equal to one month in duration, they must have 2 therapeutic INRs 4 weeks apart to begin the extended INR interval protocol.

If at any time a participant reports or clinic staff are alerted to a thromboembolic event, it will be documented in the EMR. The participant will be removed from the extended follow-up interval and not be eligible to qualify for the extended follow-up interval for 6 months after the event.

If at any time, anticoagulation clinic study staff do not feel it is appropriate to continue a participant with an extended follow-up interval, the participant can return to usual care. If at any time, the participant does not want to continue with an extended follow-up interval, they can return to usual care.

A participant will no longer be eligible for an extended INR interval if they meet any of the exclusion criteria at any time during the study, except for a bleeding or thromboembolic event. If a major bleeding or thromboembolic event occurs, they will be eligible to requalify after being on a stable warfarin dose for 6 months. A patient will also no longer be eligible for the extended INR interval if their INR goal changes and is no longer 2-3. A participant will be withdrawn from the study and no more data collected from the participant if they withdrawal their consent for the study or if death occurs.

A data monitoring committee will review the data collected, including bleeding and thromboembolic events for safety, protocol violations, and feasibility data at six months after the last patient is enrolled (at 3 months or when the 75th patient is enrolled), and then annually. If the data monitoring committee feels that the study is safe to continue, the study will continue until patients have been enrolled in the study for 2 years.

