Adverse events (AEs) collected for this study only include bleeding and thromboembolic events. Serious adverse events (SAEs) will be documented per VA and IRB definitions. AEs will be entered into OnCore after the retrospective review of the medical record at 6, 12, and 24 months after participant enrollment in the study. SAEs are entered into the SAE documentation area in OnCore as they occur, which may not align with the time period for the chart review. The SAEs that include bleeding or thromboembolism will be entered in real-time to the AE table in OnCore.

Measures: The outcomes of this study include feasibility, safety, and acceptability of extending the interval of INR follow-up to 12 weeks in stable warfarin patients. We propose to use the following measures:

1. Feasibility: We will examine the following:
 - a. Rates of participant accrual (patient interest in participating and reasons for not participating). Number of withdrawals and reasons for withdrawal from protocol or study.
 - b. Change in frequency of appointments from baseline
 - c. Frequency and type of protocol deviations from both participants and study staff
 - d. Frequency of time outside of extended INR interval protocol and why
 - e. Knowledge assessment of study staff regarding study protocol
2. Safety: We will examine the following:
 - a. Participant reported and EMR review of bleeding events. Study participant bleeding events for 12 months prior to enrollment and during the study will be compared to the clinic's bleeding event rate. The following definitions will be used to categorize bleeding:
 - i. Major
 1. Fatal or symptomatic bleed into a critical area or organ
 2. Bleeding leading to hospitalization
 3. Transfusion of 2 units or more PRBCs
 - ii. Serious
 1. Bleeding leading to ED or UC visit or additional testing
 - b. Participant reported and EMR review of thromboembolic events that are objectively verified. Study participant thromboembolic events for 12 months prior to study enrollment and during the study will be compared to the clinic's thromboembolic event rate.
 - c. Participant reported and EMR review of healthcare utilization: hospitalizations, ED visits, urgent office visits, telephone triage related to anticoagulation. Utilization for 12 months prior to study enrollment will be compared to utilization during study enrollment.
 - d. Baseline TTR (12 months prior and 6 months prior) for each patient and during study¹⁴
 - e. Number of extreme INRs (<1.5, ≥4.5)

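### The 12-month event baseline for Aim 2 contains 6 months that eligibility has cleared of treated bleeds and thromboembolism, so the before-after rate ratio is about 2.0 under constant hazard with no true effect

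*Combined protocol and SAP*

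**What the plan says.** The Aim 2 hypothesis (Specific Aims) is that there will be no difference in "bleeding and thromboembolic events from baseline (12 months prior to study enrollment) to events/year at 6, 12, and 24 months". The exclusion criteria (Participants) bar patients with a "history of bleeding or thromboembolism requiring medical intervention within past 6 months". The inclusion criteria require a "stable weekly warfarin dose for the past 6 months" and 12 months as a patient of the clinic, so the whole baseline year is observed but only its second half is selected for stability.

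The definition of a major bleed (Safety) includes "Bleeding leading to hospitalization", transfusion of at least 2 units, and fatal or symptomatic critical-site bleeding. A serious bleed is one leading to an emergency or urgent care visit or to additional testing. On study, a participant who has an event remains under observation: the Safety section ends follow-up, with "no more data collected from the participant if they withdrawal their consent for the study or if death occurs".

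The same window recurs in Measures. Item 2a reads "Study participant bleeding events for 12 months prior to enrollment and during the study will be compared to the clinic's bleeding event rate", item 2b does the same for thromboembolism, and item 2c reads "Utilization for 12 months prior to study enrollment will be compared to utilization during study enrollment". The Analysis section names McNemar, paired t and Wilcoxon signed-rank tests for change from baseline. It does not say which applies to events, and it contains no adjustment, shorter event baseline or caveat.

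**The concern.** A before-after comparison needs both periods to be open to the same events. Here the last 6 baseline months cannot contain a bleed or thromboembolism that required medical intervention, because a patient who had one could not enrol. Most major bleeds and thromboembolic events would meet that description. Serious bleeds that led only to additional testing might not. The on-study period has no such restriction.

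With no effect of the longer interval, the on-study rate would then be expected to look higher than baseline. That matters because safety is a stated aim with an explicit before-after hypothesis, and the Sample Size section intends the results to inform larger studies. The comparison of participants' pre-enrolment events with the clinic rate is affected too: participants would look lower-risk partly by construction.

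One feature works the other way. Months 7-12 before enrolment are not selected for a stable dose, and the Background reports that "bleeding and thromboembolic events were significantly lower with stable patients compared to the other patients on warfarin". The hazard in those months may therefore have been higher than on study.

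**Working it through.** **Inputs.** The 2013 clinic rates (Safety section) are major bleed 1.88%, serious bleed 0.5% and thromboembolism 0.22%. Planned enrolment is 75. The plan states no before-after ratio or power figure to reproduce. The clinic rates are consistent with exact binomial intervals on about 1,810 patients: 34 events give 1.88% (1.30-2.62%), 9 give 0.50% (0.23-0.94%) and 4 give 0.22% (0.06-0.56%; the protocol prints 0.6%).

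**Base case: constant hazard, every event triggers the exclusion.**
- Rate: 1.88% + 0.22% = 2.10% per year.
- On study: 75 × 0.0210 = 1.58 events per year.
- Baseline year: 75 × 0.0210 × 0.5 = 0.79 events, or 1.05%.
- Ratio under no effect: 2.10 / 1.05 = 2.0. Simulation with patient-to-patient variation in risk leaves this at 2.0.

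**Relaxing the assumptions.** Let h be the months 7-12 hazard divided by the on-study hazard, and f the share of events that do not trigger the exclusion. Neither is given in the documents. The ratio under no effect is 2/(h + f) with the 12-month baseline and 1/h with months 7-12 alone.

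| h | f | 12-month baseline | Months 7-12 only |
|---|---|---|---|
| 1 | 0 | 2.00 | 1.00 |
| 1 | 0.1 | 1.82 | 1.00 |
| 1 | 0.5 | 1.33 | 1.00 |
| 1.25 | 0 | 1.60 | 0.80 |
| 1.25 | 0.1 | 1.48 | 0.80 |
| 1.5 | 0 | 1.33 | 0.67 |
| 2 | 0 | 1.00 | 0.50 |
| 2 | 0.5 | 0.80 | 0.50 |

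An earlier hazard below the on-study one would push the 12-month ratio above 2 (4.0 at h = 0.5, f = 0).

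**Adding serious bleeds, none excluded.** On study: 75 × 2.60% = 1.95. Baseline: 75 × (0.5 × 2.10% + 0.50%) = 1.16. Ratio: 1.68.

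**Fatal events.** These cannot occur in the baseline of an enrolled patient. For an assumed fatal share d, the base-case ratio is 2/(1 - d): 2.1 at 5% and 2.5 at 20%.

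**Effect on a test.** With the 12-month baseline, constant hazard and a two-sided 5% level (assumed; the plan gives none), an exact conditional rate test that doubles the smaller tail rejects in about 0.3% of trials at 12 months and 0.1% at 24 months. Exact McNemar on 12-month windows rejects in 0.24% with the cleared baseline and 0.22% without.

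**Precision of months 7-12.** Person-time falls from 75 to 37.5 years. The probability of no major bleed or thromboembolism there is exp(-0.7875h): 0.45 at h = 1 and 0.21 at h = 2. As an example, take 1 event in months 7-12, none in the last 6 months, and 3 over 24 months on study (150 person-years):
- against months 7-12: (3/150)/(1/37.5) = 0.75, exact 95% CI 0.06 to 39;
- against 12 months: (3/150)/(1/75) = 1.50, exact 95% CI 0.12 to 79.

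**The case against.** The strongest reply is that little depends on this contrast. The study is about feasibility and claims no power. The distortion is under one event per year, and the McNemar rejection probability barely moves. Stopping rules and committee review count on-study events, and the on-study comparison with the clinic rate does not touch the cleared window. All of that stands, and it limits the severity. It does not remove the bias: when testing has almost no power, the descriptive estimate is the main product of the safety aim, and that estimate is what is distorted.

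The second reply is that the net direction is not established, since a higher hazard in months 7-12 could cancel or reverse the bias. This also stands in part. Only the direction of the selection is certain. Full cancellation needs h + f to reach 2, for instance a doubled earlier hazard, and nothing in the documents shows that. The 0.8 event also applies a whole-clinic rate to stable patients, so the true number may be smaller; the ratio does not depend on that rate.

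The third reply is that months 7-12 make a weak baseline: sparse, often empty, and leaning towards apparent benefit if h exceeds 1. That is correct, and it is why both windows should be shown rather than one substituted for the other.

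**Conclusion.** The concern holds and should be fixed. The overlap between the baseline year and the 6-month exclusion is plain from the text and is uncorrected. For major bleeds and thromboembolism the expected before-after ratio with no true effect is 2.0, given constant hazard and every event triggering the exclusion. It stays above 1 whenever h + f is below 2. Confidence is high for the direction of the selection and moderate for the factor of 2, because h, f and the fatal share are assumptions.

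The consequence is a biased descriptive estimate for Aim 2 and a biased comparison of pre-enrolment events with the clinic rate, not a material risk of a false significant result. Utilisation related to bleeds or thromboembolism shares the problem. Time in therapeutic range (TTR) is probably affected in the same direction, but eligibility restricts dose changes rather than INRs, and the size cannot be computed from the documents.

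**What to change.** Amend Aim 2, Measures 2a-2d and the Analysis section as follows.

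- Compare events as rates per person-time with exact 95% intervals, counting on-study time to withdrawal or death.
- Use months 7-12 before enrolment as the event baseline and report the full 12-month baseline beside it. State that the last 6 months are free of treated events by selection, and that months 7-12 may precede dose stability, so that contrast can err towards benefit. In expectation the two ratios bracket 1.0 under no effect when h is at least 1 and h + f is at most 2; neither window is unbiased alone.
- Report fatal events separately, and treat utilisation related to bleeds or thromboembolism in the same way.
- If McNemar is applied to events, use windows of equal length.
- For TTR, keep the 12-month baseline, add months 7-12 as a sensitivity analysis, and do not use the 6-month-prior value as the comparator.
- Label the before-after event comparisons descriptive.

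The cost is wording only; records for the 12 months before enrolment are already to be collected. The price is precision, as shown above. The descriptive label is needed because, with no true effect, a test against months 7-12 at 24 months would point falsely to benefit in about 0.5% of trials at equal hazard and 4.5% at twice the hazard. With the minimum-likelihood form of the exact test those figures are 1.8% and 8.8%.

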Patients will be prescreened for study eligibility. Patients must have an INR goal of 2-3, be on indefinite warfarin therapy, and be on a stable warfarin dose for at least 6 months, except for a single, one-time adjustment. Planned procedures with INR(s) out of range would not exclude a patient. All participants will be provided usual care from the anticoagulation clinic, including a thorough INR assessment and plan for warfarin. The exception to usual care is the duration of follow-up. If the participant continues to be on a stable dose of warfarin and the INRs are within the goal range of 2-3 (including lab variation), follow-up visits will be scheduled following the extended interval protocol, which includes visits at 5-6 weeks, then 7-8 weeks, and then 11-12 weeks. If a situation arises where the extended interval is no longer appropriate (e.g. single INR outside of goal range and lab variation, a participant has a procedure requiring interruption of warfarin, drug interaction, hospitalization, etc.), the issue will be managed per usual care. If there was a permanent weekly dose adjustment or if the temporary dose change was more than 1 month, the participant would return to usual clinic care. They could requalify for the extended interval protocol when they have been on the same warfarin dose for at least 6 months, except for a single, one-time adjustment. Planned procedures with INR(s) out of range would not exclude a patient. If there was not a permanent weekly dose adjustment or if the temporary dose change was less than or equal to one month, two therapeutic INRs 4 weeks apart will be needed prior to starting the participant on the extended interval. Patient satisfaction will be evaluated at baseline, 6, 12, and 24 months. Additionally provider satisfaction, confidence, and knowledge of the extended interval protocol will be evaluated at baseline and at the end of the study. A chart review will be conducted to evaluate adherence to the extended interval protocol by study staff, including inadvertent protocol violations. Bleeding and thromboembolic events will be evaluated to ensure the safety of an extended follow-up interval.

Specific Aims:

1. To determine the feasibility of implementing an extended interval of INR follow-up in Veterans on a stable dose of warfarin.

Goal: We aim to enroll 75 patients within 3 months.

Goal: The anticoagulation pharmacy staff will be able to accurately follow the extended interval protocol.

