The events rates for 2013 clinic data are listed below, including a 95%CI. Additionally, ranges for event rates over the past 4 years are included.

- Major bleed: 1.88% (95%CI 1.3-2.62%); range of 1.8-2%
- Serious bleed: 0.5% (95%CI 0.23-0.94%); range of 0-0.5%
- Thromboembolism: 0.22% (95%CI 0.06-0.6%); range of 0.2-0.44%

Stoppage rules for the study:

1. Stoppage rules for the study (based on event rates from the Schulman, et al. article) are included below. If the study is stopped early, all subjects will be scheduled for an INR within 6 weeks of their last INR, which is usual practice for the clinic.

Data from Schluman study				Madison VA	
Event	# from Schulman study	Rate per 1 year	95%CI of the 1 year rate from Schulman	Approx Count Based on 50 patients enrolled using upper end of 95% CI	Stoppage of Study
TE (includes TE-related death)	4	1.6%	0.4-4	2	3
Composite of TE, TIA, and major bleeding, TE-related death	12	4.8%	2.5-8.2	4.1	5

2. If an event occurs:
 - a. The PI or one of the Co-PIs will thoroughly evaluate the event to determine if it was related to study participation. . The following chart will be used to determine if the event was related to study participation.

Bleeding or TE event [‡]	On Extended Interval at Time of Event or within 6 Weeks of Event	INR Measure at visit following extended interval and/OR at Time of Event	Relationship to Hemostasis (as relates to INR direction/ magnitude)	Level of Attribution
Yes	Yes	Within target range	-	Possible
Yes	Yes	Outside target range	No relationship or uncertainty	Possible
Yes	Yes	Outside target range	Possible relationship	Probable
Yes	Yes	Outside target range	Definite relationship	Definite*

*Stopping rules apply to the events with a definite attribution. (Additional events may apply based on the discretion of the DMC and IRB.)

[‡] If the event was due to accident, injury, or other clear cause, attribution may not follow table.

- b. If a patient has a major bleeding or thromboembolic event, our protocol states that the patient will return to usual care and must be on the same dose for 6 months until they are able to requalify for the extended INR interval.

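### The stopping counts of 3 thromboembolic and 5 composite events are derived for 50 patients over one year, the plan is up to 75 patients over two years, and neither the 50 nor the counting period is explained

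*Combined protocol and SAP*

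**What the plan says.** The stoppage table (Procedures, Safety) takes one-year event rates and 95% confidence limits from a cited randomised trial. It converts the upper limits to counts under the heading "Approx Count Based on 50 patients enrolled using upper end of 95% CI". For TE the upper limit is 4%, the count 2 and the stopping count 3. For the composite they are 8.2%, 4.1 and 5.

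The rest of the protocol describes a different exposure:

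- Specific Aims, Aim 1: "We aim to enroll 75 patients within 3 months".
- Participants: "We propose to enroll 75 eligible patients on warfarin".
- Patient identification: if the target is missed, "additional patients may be enrolled if 75 patients were not initially enrolled", after a safety review.
- Safety, data monitoring committee (DMC): reviews fall "six months after the last patient is enrolled (at 3 months or when the 75th patient is enrolled), and then annually". If the DMC is satisfied, "the study will continue until patients have been enrolled in the study for 2 years".

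The attribution table then restricts what counts. Its footnote reads "Stopping rules apply to the events with a definite attribution", with the DMC and IRB free to add events. One of its columns is "On Extended Interval at Time of Event or within 6 Weeks of Event". That column classifies a single event; it does not define a period over which events accumulate.

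**The concern.** A fixed stopping count stands for a rate only when it is tied to an exposure. This table's exposure is 50 patients for one year, which matches neither the planned number nor the planned duration. As no counting period is given, two careful readers can apply the rule with opposite results. Three composite events in the first year and two in the second reach a cumulative count of 5 but not an annual one.

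This is the only numerical stopping threshold in the protocol. A reader who meets 5 events late in follow-up cannot tell whether the sponsor meant that to signal an excess over the reference trial.

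**Working it through.** **Inputs.** From the stoppage table: TE, 4 events, 1.6% per year, upper limit 4%, stop at 3; composite, 12 events, 4.8% per year, upper limit 8.2%, stop at 5. From Participants and the DMC paragraph: 75 patients, 2 years. From the 2013 clinic rates listed just above the stopping rules: TE 0.22%, major bleeding 1.88%.

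**Step 1: reproduce the table.** Count = patients x years x upper limit. 50 x 1 x 0.04 = 2.0, and the next whole number is 3. 50 x 1 x 0.082 = 4.1, and the next whole number is 5. Both match; the next-whole-number step is inferred, not stated. The denominators are 4/0.016 = 250 and 12/0.048 = 250. Exact limits on 4/250 and 12/250 are 0.44-4.05% and 2.50-8.23%, which agree with the printed intervals.

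**Step 2: apply the same formula to other bases** (PY = patient-years).

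| Basis | PY | TE (4%) | Composite (8.2%) |
|---|---|---|---|
| 50 patients x 1 year (table) | 50 | 2.0 | 4.1 |
| 75 x 1 year | 75 | 3.0 | 6.15 |
| 50 x 2 years | 100 | 4.0 | 8.2 |
| 75 x 2 years | 150 | 6.0 | 12.3 |

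The printed 3 and 5 exceed the formula on the first row only.

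**Step 3: where a cumulative count stops exceeding the formula.** TE: 3/0.04 = 75 PY. Composite: 5/0.082 = 61 PY. Five composite events are 5/50 = 10.0% per year at 50 PY, 5/75 = 6.7% at 75 PY and 5/150 = 3.3% at 150 PY. They equal the 4.8% reference at 5/0.048 = 104 PY.

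**Step 4: place the DMC reviews.** Assume 75 patients enrolled evenly over 3 months and no losses. Exposure at month t (from month 3) is 75 x (t - 1.5)/12. The first review, at month 9, falls at 75 x 7.5/12 = 46.9 PY, where the formula gives 1.88 / 3.84. The next, at month 21, falls at 75 x 19.5/12 = 121.9 PY, giving 4.88 / 9.99.

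**Step 5: chance of reaching 3 TE / 5 composite events** (Poisson, cumulative count, each threshold taken separately).

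| Assumed true rate and share of events counted | PY | TE | Composite |
|---|---|---|---|
| Cited trial (1.6% / 4.8%), all | 50 | 4.7% | 9.6% |
| Cited trial, all | 150 | 43% | 84% |
| Cited trial, 75% (assumed) | 150 | 27% | 63% |
| Cited trial, 25% (assumed) | 150 | 2.3% | 3.6% |
| Clinic 2013 (0.22% / 2.10%), all | 150 | 0.5% | 21% |

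The clinic composite is taken as 0.22 + 1.88 = 2.10%, since TIA is not listed separately. The share of events that would be countable is not given in the documents, so 25% and 75% are only illustrations. At the cited rates, a share of 50/150 = one third at 150 PY reproduces the table's own 4.7% / 9.6%.

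**The case against.** **50 may be a realistic enrolment, and the table fits the first review.** Recruitment may end below 75, and exposure at the first DMC review, about 47 PY on the assumption above, is close to 50. But the protocol gives neither as the reason, and the table is not labelled as applying to one review. Even 50 patients give 100 PY over 2 years.

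**Cumulative is the ordinary reading.** The table has no reset or per-year wording, so this is fair. It narrows the ambiguity but does not remove the mismatch: under that reading the counts fall below the formula's own limits from 61 and 75 PY.

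**An early stop of a feasibility study is the safe direction.** A reader might infer that the rule is simply too strict, with an 84% chance of an unwarranted stop, and that the counts should rise. The documents do not support this. The 84% assumes that the cited trial's rates apply and that every event counts. The clinic's own rates give 0.5% / 21%, and the definite-attribution filter lowers all these figures by an unknown amount. The reference rates are the full listed counts over 250 with no such filter shown, so the filter and the mismatch pull in opposite directions.

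**A threshold scaled to exposure at each event would be worse.** This stands. With upper limit x PY applied at each event date, the TE limit is below 1 until 1/0.04 = 25 PY, so a single countable TE event before then would stop the study. Simulated to 150 PY at the cited rates, that rule crosses for TE in about 10% against 2.3% for the fixed count at a 25% share, and in 30% against 27% at a 75% share.

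**Other safeguards exist.** The DMC judges safety independently and, with the IRB, may count further events. That limits the harm but does not say what the counts represent.

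**Conclusion.** The mismatch is established from the text alone: the thresholds are computed for 50 patient-years, the plan allows up to 150, and neither the 50 nor the counting period is explained. There is no arithmetic error in the table; it is correct for the basis in its heading.

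The size is a factor of three between the table's basis and full planned exposure (2.0 / 4.1 against 6.0 / 12.3). Read cumulatively, 5 composite events lie below the table's own reference rate beyond 104 PY. These figures rest only on the table's formula and the planned numbers, taking 150 PY as a maximum with no losses.

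The effect on the chance of stopping is not established. It depends on the true event rates and on the share of events judged definite, and the protocol does not fix that share. The net direction, too strict or too lax, therefore stays open. This should be fixed before the rule is relied on, but individual-patient safeguards and DMC review remain in place meanwhile.

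**What to change.** Reconcile the stoppage table with Aim 1, Participants, Patient identification and the DMC paragraph:

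1. Re-derive the table with the sponsor's own formula on the planned enrolment and a stated counting period, for example one row per scheduled DMC review at the exposure expected by then. Alternatively, state why 50 patients and one year is the intended basis.
2. State whether the counts are cumulative or annual.
3. Note that the reference rates are not shown as restricted to events of definite attribution. The sponsor and DMC should settle that difference before any count is changed.

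No replacement count is proposed, and no threshold recalculated at each event. The choice of limit belongs to the sponsor and DMC.

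The cost is one amended table and two added sentences. The downside is that the threshold may no longer be a single fixed count.
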